5.5.3.3. DoR and iDoR

The DoR and iDoR are defined as the time until progression of disease or death for patients with PR, iPR or CR, iCR and will be summarized using Kaplan-Meier estimates in the efficacy population. Responders will be considered to have an ongoing response if they:

- have not progressed, and
- have not started a next-line anti-cancer therapy, and
- have not been lost to follow-up, and
- are alive.

Patients with missing data will be censored/considered as having an event as specified in the table below.

Table 4 DoR and iDoR events and censoring

Situation	Date of progression or censoring	Outcome
No progression, no death. No start of next-line anti-cancer therapy.	Date of the last evaluable tumor assessment.	Censored
No progression, no death. Start of next-line anti-cancer therapy.	Date of the last tumor assessment with non-progression before the start of next-line anti-cancer therapy.	Censored
Progression or death after one missed adequate tumor assessment.	Date of progression or death, whichever is earliest (if both occur).	Progressed
Progression or death after more than one missed adequate tumor assessment.	Date of the last evaluable tumor assessment.	Censored

For DOR, the start date is the date of first documented response of CR or PR (i.e. the start date of response, not the date when response was confirmed), and the end date is defined as the date of the first documented progression or death.

For iDOR, the start date is the date of first documented response of iCR or iPR (i.e. the start date of response, not the date when response was confirmed), and the end date is defined as the date of the first documented progression according to iRECIST or death.

The progression date to be used for calculation of iDOR should be the first date at which progression criteria are met (i.e, the date of iUPD) provided that iCPD is confirmed at the

next assessment. If iUPD occurs, but is disregarded because of later iSD, iPR, or iCR, that iUPD date should not be used as the progression event date.

If progression is not confirmed and there is no subsequent iSD, iPR, or iCR, the iUPD date should still be used if:

- the patient stops protocol treatment because they were not judged to be clinically stable, or
- no further tumor assessments are done, or
- the next timepoint responses are all iUPD, and iCPD never occurs, or
- the patient dies from his cancer.

DOR according to RECIST and iRECIST will be presented in a data listing for ASaT population.

DOR according to RECIST and iRECIST will be presented graphically using Kaplan-meier plots for efficacy and ASaT populations including count for numbers of patients at risk.

5.5.3.4. CBR and iCBR

The CBR and iCBR are defined as the number of PR, iPR, CR, iCR, and SD, iSD and will be analyzed in the efficacy population and presented as a point estimate along with 95% Clopper-Pearson CI. SD, iSD needs to last at least 6 weeks from the start of study treatment; if not, at least one follow-up scan is required to declare stable disease. Patients with missing data will be considered as non-responders.

The analysis will be repeated for ASaT and PP populations as well as in the efficacy population where patients with missing data will be excluded from the analysis.

CBR according to RECIST and iRECIST will be presented in a data listing for ASaT population.

5.5.3.5. PFS and iPFS

PFS and iPFS are defined as the time from the first day of study treatment until the first date of radiological disease progression or death and will be summarized using Kaplan-Meier estimates in the efficacy population.

Patients with missing data will be censored/considered as having an event as specified in the table below.

Table 5 PFS and iPFS events and censoring

Situation	Date of progression or censoring	Outcome
Incomplete or no baseline tumor assessment.	First day of study treatment	Censored

Start of next-line anti-cancer therapy.	Date of the last tumor assessment with non-progression before the start of next-line anti-cancer therapy.	Censored
Death before the first disease progression assessment.	Date of death.	Progressed
Death between adequate tumor assessment visits.	Date of death.	Progressed
Progression or death after one missed adequate tumor assessment.	Date of progression or death, whichever is earliest (if both occur).	Progressed
Progression or death after more than one missed adequate tumor assessment.	Date of the last evaluable tumor assessment.	Censored
No progression, no death.	Date of the last evaluable tumor assessment.	Censored

For iPFS, the progression date to be used for calculation should be the first date at which progression criteria are met (i.e, the date of iUPD) provided that iCPD is confirmed at the next assessment. If iUPD occurs, but is disregarded because of later iSD, iPR, or iCR, that iUPD date should not be used as the progression event date.

If progression is not confirmed and there is no subsequent iSD, iPR, or iCR, the iUPD date should still be used if:

- the patient stops protocol treatment because they were not judged to be clinically stable, or
- no further tumor assessments are done, or
- the next timepoint responses are all iUPD, and iCPD never occurs, or
- the patient dies from his cancer.

PFS according to RECIST and iRECIST will be listed for ASaT population.

PFS according to RECIST and iRECIST will be displayed graphically using Kaplan-meier plots for efficacy and ASaT populations including count for numbers of patients at risk.

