7 DISCONTINUATION OF STUDY INTERVENTION AND PATIENT DISCONTINUATION/WITHDRAWAL

7.1 Discontinuation of study intervention

Discontinuation of study treatment does not represent withdrawal from the study.

A patient must be discontinued from study treatment for any of the following reasons:

- Confirmed radiographic disease progression as specified in section [10.2.7](#).
- Clinical disease progression (investigator's assessment)
- AE, namely intercurrent illness or study treatment-related toxicity that would, in the judgment of the investigator, affect assessments of the patient's clinical status to a significant degree or require discontinuation of study treatments
- Pregnancy of the patient
- Concomitant treatment with a prohibited medication
- Initiation of new systemic anti-cancer therapy
- Patient's decision
- Investigator's decision

After discontinuation of nanrilkefusp alfa and/or cetuximab (whichever occurs later), all patients will be followed up in the study as described in section [4.1.4.3](#).

If nanrilkefusp alfa needs to be stopped, patients will discontinue cetuximab as well. Such patients will receive standard of care treatment outside the clinical trial.

If cetuximab needs to be stopped due to an AE or the patient's or investigator's decision, nanrilkefusp alfa treatment can continue until any of the criteria for stopping or discontinuation of study treatment listed above is met. If cetuximab needs to be stopped for any of the reasons listed above except for an AE or the patient's or investigator's decision, nanrilkefusp alfa needs to be discontinued as well.

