8.1.3 End of treatment and follow-up tumor imaging

If patients discontinue study interventions, tumor scans should be performed at the time of discontinuation (± 4 -week window) unless previous scans were obtained within 4 weeks of discontinuation.

If patients discontinue study interventions without documented disease progression, every effort should be made to monitor disease status by acquiring tumor scans using the same schedule used while on treatment (every 6 weeks [± 2 weeks]).

Scans are to be continued until:

- Confirmed disease progression per iRECIST

- Start of next-line anti-cancer treatment
- Pregnancy of the patient
- Withdrawal of consent by the patient
- End of the study

All imaging assessments need to have confirmatory imaging using the identical method after at least 4 weeks.

Patients who are clinically stable and treated past radiographic progression may continue to be assessed until progression is confirmed according to the rules of iRECIST, when clinically appropriate.

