5.5. Efficacy

Only tumor assessments prior to or at the date of initiation of further-line therapy and using CT scan or MRI will be used for the evaluation of tumor response.

In case of a confirmed response or disease progression, the date of the first tumor assessment evaluated as response or progression will be used for the time-to-event variables.

Up to the first iUPD, the RECIST 1.1 disease response assessment will be derived from the iRECIST response assessment form as follows:

Table 2 Derivation of RECIST 1.1 Disease Response from iRECIST 1.1

iRECIST	RECIST 1.1
iCR	CR
iPR	PR
iSD	SD
iUPD	PD
Non-iCR/Non-iUPD	Non-CR / Non-PD
NE	NE

After the first iUPD, the RECIST 1.1 overall response will no longer be derived.

All efficacy data endpoint will be listed on the enrolled population, with the exception of time to event analyses where the ASaT population will be used.

Overview of Tumor Assessments with a swimmer plot per RECIST 1.1 and iRECIST 1.1 will be displayed graphically for ASaT population.

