5.5.3.7. TtP and iTtP

TtP and iTtP are defined as the time from the first day of study treatment until the first date of radiological disease progression and will be summarized using Kaplan-Meier estimates in the efficacy population.

Patients with missing data will be censored/considered as having an event as specified in Table below.

Table 6 TtP and iTtP events and censoring

Situation	Date of progression or censoring	Outcome
Incomplete or no baseline tumor assessment.	First day of study treatment	Censored
Start of next-line anti-cancer therapy.	Date of the last tumor assessment with non-progression before the start of next-line anti-cancer therapy.	Censored
Death before the first disease progression assessment.	Date of death.	Censored
Death between adequate tumor assessment visits.	Date of death.	Censored
Death after one missed adequate tumor assessment.	Date of death.	Censored
Progression after one missed adequate tumor assessment.	Date of progression.	Progressed
Progression after more than one missed adequate tumor assessment.	Date of the last evaluable tumor assessment.	Censored
No progression.	Date of the last evaluable tumor assessment.	Censored

For iTtP, the progression date to be used for calculation should be the first date at which progression criteria are met (i.e, the date of iUPD) provided that iCPD is confirmed at the next assessment. If iUPD occurs, but is disregarded because of later iSD, iPR, or iCR, that iUPD date should not be used as the progression event date.

If progression is not confirmed and there is no subsequent iSD, iPR, or iCR, the iUPD date should still be used if:

- the patient stops protocol treatment because they were not judged to be clinically stable, or
- no further tumor assessments are done, or
- the next timepoint responses are all iUPD, and iCPD never occurs, or
- the patient dies from his cancer.

TtP according to RECIST and iRECIST will be listed for ASaT population.

TtP according to RECIST and iRECIST will be displayed graphically using Kaplan-meier plots for efficacy and ASaT populations including count for numbers of patients at risk.

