5.5.4. Sensitivity Analyses for the Secondary Efficacy Analysis

Secondary efficacy analysis will be repeated for ASaT population.

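### Patients who stop for clinical progression and start next-line therapy without radiological PD are censored in PFS, TtP and DoR; to the extent they occur the estimates run high, and no planned analysis varies this rule

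*SAP*

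**What the plan says.** Protocol 7.1 lists "Clinical disease progression", on the investigator's assessment, among the reasons for which treatment must stop. No scan evidence is required.

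The event definitions in the SAP are narrower. PFS and iPFS (5.5.3.5) run "until the first date of radiological disease progression or death". TtP and iTtP (5.5.3.7) run "until the first date of radiological disease progression and will be summarized using Kaplan-Meier estimates". DoR and iDoR (5.5.3.3) end at progression or death. The word radiological is absent there, but RECIST response is derived from the tumor response form (5.5, Table 2) and Table 4 has no row for clinical progression.

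Tables 5 and 6 censor a patient who starts next-line therapy at the "Date of the last tumor assessment with non-progression before the start of next-line anti-cancer therapy". Table 4 does the same for responders in the situation "No progression, no death. Start of next-line anti-cancer therapy". Protocol Tables 9.1 to 9.3 agree.

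A later scan cannot restore the event. Protocol 8.1.3 ends scanning at "Start of next-line anti-cancer treatment", and SAP 5.5 states "Only tumor assessments prior to or at the date of initiation of further-line therapy and using CT scan or MRI will be used" for response evaluation.

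The sensitivity plan for these endpoints is one sentence, SAP 5.5.4: "Secondary efficacy analysis will be repeated for ASaT population". Protocol 9.3.5 leaves further sensitivity analyses to the SAP, which adds none that varies the censoring.

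**The concern.** Kaplan-Meier treats a censored patient as having the same future risk as those still under observation. A patient taken off treatment because the investigator saw clinical progression, and then given another anti-cancer therapy, is unlikely to meet that assumption. Censoring at the last non-PD scan removes the patient from the risk set just before the likely event, and the curve stays too high.

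With one arm, such a bias cannot cancel between groups. Protocol 4.2 says the study looks for preliminary efficacy signals to support a confirmatory trial, and PFS and DoR will inform that reading. Repeating the analysis in ASaT changes who is counted, not how these patients are handled.

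**Working it through.** **The plan's own figures.** The documents state no PFS, TtP or DoR value, so there is none to reproduce. The sample-size statement holds: with a uniform prior and 19 responses in 52 (0.368 × 52 = 19.1), the posterior probability that ORR exceeds 28.8% is 0.899. Averaged over Binomial(52, 0.368) it is 0.819. Both meet the stated 80%. The futility limit also holds: the exact 80% upper limit is 22.2% for 1/16 and 30.0% for 2/16, so fewer than 2 is the right boundary. Neither calculation uses the censoring rules.

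**Inputs for the illustration.**
- Scan interval: 42 days (Protocol 8.1.2), which is 42/30.4375 = 1.380 months.
- Latent median *M*: assumed 3, 4 or 6 months, exponential.
- Share *f* of progressions that are clinical only and followed by next-line therapy before the next scan: assumed 0 to 30%.
- No capture by a discontinuation scan.

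**Formula.** The chance of progressing within one scan interval is p = 1 − 2^(−1.380/M). Four scans (day 168) fall before 6 months. If every progression were seen at the next scan, 6-month PFS = (1 − p)^4. Under Table 5, a fraction *fp* leaves the risk set at the preceding scan, and of the remaining 1 − *fp* a fraction (1 − *f*)*p* have events. Each Kaplan-Meier factor is therefore (1 − p)/(1 − fp), and

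Table 5 estimate = (1 − p)^4 / (1 − fp)^4.

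For *M* = 4 and *f* = 20%: p = 0.2127, (1 − p)^4 = 0.384, 1 − fp = 0.9575, and 0.384/0.9575^4 = 0.457.

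| M (months) | p | f = 0 | f = 10% | f = 20% | f = 30% |
|---|---|---|---|---|---|
| 3 | 0.273 | 27.9% | 31.2% | 35.0% | 39.3% |
| 4 | 0.213 | 38.4% | 41.9% | 45.7% | 50.0% |
| 6 | 0.147 | 52.8% | 56.1% | 59.6% | 63.3% |

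The overstatement is 3.2 to 3.5 points at 10%, 6.7 to 7.3 at 20% and 10.5 to 11.6 at 30%. Simulation gives the same values within rounding.

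The simulation also counted clinical progression or next-line start as an event. For *M* = 4 this gave 38.1%, 37.8% and 37.3% at the three shares, so the gap to Table 5 is 3.8, 7.9 and 12.6 points. It is slightly wider because those events are dated before the next scan.

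**Scale.** At n = 52 the simulated sampling SD of 6-month PFS is about 7 points, so a 20% share would shift the estimate by about one SD. With a constant hazard and continuous observation, the median is inflated by 1/(1 − f): 1.11, 1.25 and 1.43. On a six-weekly grid it moves in steps of 1.38 months, so 6-month PFS is the clearer measure.

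**Partial capture.** Protocol 8.1.3 waives the discontinuation scan if one was done within 4 weeks. If discontinuations fall evenly across a 6-week interval (an assumption), 4/6 are waived. If every remaining patient were scanned and showed PD, a 20% share would fall to 20% × 4/6 = 13.3%. The formula then gives 4.4 to 4.7 points for the three medians.

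TtP and DoR were not quantified. The mechanism is the same, but no figure is offered for them.

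**The case against.** The affected group is smaller than the censoring tables suggest. Protocol 8.1.3 asks for a scan around discontinuation and for continued six-weekly scans in patients who stop without documented progression. Protocol 8.1 collects unscheduled scans that show progression. SAP 4.1.4 admits all tumor assessments to the time-to-event analysis, and under Table 2 a single iUPD is already a RECIST PD. Deaths without next-line therapy are PFS events, subject to the missed-assessment row. This stands: only a residual group is affected, namely those with clinical progression, no PD on any scan up to next-line start, and next-line therapy. It does not empty that group. The discontinuation scan has a ±4-week window and a waiver, and all scanning ends when next-line therapy starts. The iRECIST rule that counts an unconfirmed iUPD when a patient stops for clinical instability still needs a radiological iUPD.

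A reader might infer that nothing planned would reveal these patients. That goes too far. The SAP reports numbers censored (5.1), reasons for treatment discontinuation (5.2) and a swimmer plot (5.5), and it lists subsequent therapy and the time-to-event data. In about 52 patients they could largely be traced by hand. What is missing is a summary by censoring reason and a re-estimated curve.

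A reader might also infer that the bias flatters a comparison with historical PFS. The plan names no such comparator. Its only benchmark is an ORR of 20%, and Protocol 9.3.1 calls the analyses descriptive, without comparison.

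**Conclusion.** The point holds conditionally. Tables 4 to 6 censor the residual group at the last non-PD scan, that censoring is informative, and the only planned sensitivity analysis keeps the same rules. One might read the tables as showing that PFS, TtP and DoR are biased upward. The documents do not support that as a fact: they give no share of such patients, and at a share of zero there is no effect.

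The size given for 6-month PFS (about 3 to 4 points at a 10% share, 7 to 8 at 20%, 10 to 12 at 30%) rests on assumed medians of 3 to 6 months, exponential progression, six-weekly scans and no capture by discontinuation scans. Any capture reduces it. It is an illustration, not a forecast for this trial.

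The endpoints are secondary and descriptive. The primary ORR, the sample size and the futility rule do not depend on these tables. This is a worthwhile low-cost improvement, not a defect in the main analysis.

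**What to change.** Leave the main analysis as it is and add to SAP 5.5.4, for PFS, TtP and DoR:

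1. A sensitivity analysis that counts discontinuation for clinical progression as an event on its date.
2. A second version that also counts any start of next-line therapy without prior PD as an event. Label it a conservative bound: it includes patients who switched after toxicity or by choice, so it can err downward and is not an unbiased estimate.
3. In these analyses, for PFS and DoR, count progression or death after more than one missed assessment on its actual date. For TtP, treat only progression this way and keep death censored, because death is not a TtP event.
4. Report beside the main estimate the number of patients reclassified and the number censored by reason.

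The cost is a short SAP paragraph and one extra table, with a sensitivity estimate that may be slightly less favorable. The SAP already summarizes discontinuation reasons (5.2) and imputes partial next-line start dates (4.2.4), so the data should exist. The eCRF is not among the documents, so check that it records the reason and date of discontinuation in usable form. No trial procedure changes.

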5.5.3.6. TtR and iTtR

TtR and iTtR are defined as the time from the first day of study treatment until the first date of PR, iPR or CR, iCR and will be summarized using Kaplan-Meier estimates in the efficacy population.

Confirmed response dates will be used. Patients with missing data will be censored at the last assessment date, date of death, or date of eligibility (if incomplete or no baseline tumor assessments), whichever occurs latest.

TTR according to RECIST and iRECIST will be listed for ASaT population.

TTR according to RECIST and iRECIST will be displayed graphically using Kaplan-meier plots for efficacy and ASaT populations including count for numbers of patients at risk.

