4.1.4.1 Screening

Patients will be screened within a period of not more than 21 days, which will start when the Informed Consent Form (ICF) has been signed and end before day 1 of cycle 1.

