3.2. Enrolled Population

The enrolled population is defined as all patients who sign the main study informed consent form and all eligibility criteria are met as confirmed by approver during screening assessments.

This population may include patients who do not receive study treatment.

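### Time to response is a Kaplan-Meier estimate in all patients with no competing-event handling, so the curve can overstate how many respond

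*SAP*

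**What the plan says.** SAP 5.5.3.6 measures TtR and iTtR from the first day of study treatment to the first date of partial or complete response. Each "will be summarized using Kaplan-Meier estimates in the efficacy population", so non-responders are part of the curve. The censoring rule reads "Patients with missing data will be censored at the last assessment date, date of death, or date of eligibility", and the eligibility date is qualified by "if incomplete or no baseline tumor assessments), whichever occurs latest". Protocol 9.3.3.1 gives the same rule. Protocol 9.3.1 and SAP 5.1 add a median with 95% CI and quartiles.

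DoR, PFS and TtP each have an event and censoring table (SAP Tables 4, 5 and 6). TtR has none, and its section does not mention progression. SAP 5.5 states that the RECIST 1.1 overall response is not derived after the first iUPD.

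On the date of a response, SAP 5.5.3.6 says "Confirmed response dates will be used". The general rule in SAP 5.5 is "In case of a confirmed response or disease progression, the date of the first tumor assessment evaluated as response or progression will be used", and SAP 5.5.3.3 specifies for DoR "the start date of response, not the date when response was confirmed".

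**The concern.** Kaplan-Meier censoring assumes that a censored patient could still have the event later, at the same rate as those who remain at risk. For RECIST 1.1 response this is false after death and, under SAP 5.5, after progression. Treating these patients as censored redistributes their weight to those still under observation. One minus Kaplan-Meier then estimates the response proportion in a hypothetical setting where nobody progresses or dies.

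Two outputs are at stake. The plateau of the TtR curve can lie above the ORR reported from the same patients. The planned median can also appear to be reached although fewer than half of the patients respond, and it then describes neither responders nor the whole population.

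**Working it through.** The plan gives no TtR figure, so there is nothing to reproduce. The checks below are illustrations, and their assumptions are stated.

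**Inputs from the documents.** N = 52 (Protocol 9.5, SAP 2.3); desired ORR 36.8% (same sections); scans every 6 weeks (Protocol 8.1.2).

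**1. Worked example.** Assumed responses / progressions: 12/14 at week 6, 5/8 at week 12, 2/4 at week 18. True response proportion = (12 + 5 + 2)/52 = 19/52 = 36.5%, close to the desired ORR. The estimate depends on when a progressed patient leaves the risk set:

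| Progressed patient leaves the risk set | At risk at weeks 6, 12, 18 | 1 − KM |
|---|---|---|
| At the progression scan | 52, 26, 13 | 1 − (40/52)(21/26)(11/13) = 47.4% |
| One scan later | 52, 40, 21 | 1 − (40/52)(35/40)(19/21) = 39.1% |
| After week 18 (for example, dies later) | 52, 40, 35 | 1 − (40/52)(35/40)(33/35) = 36.5% |

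The excess is 47.4 − 36.5 = 10.9 points in the first row, 39.1 − 36.5 = 2.6 in the second and 0 in the third. None of the three rows reaches a median.

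**2. Can a false median appear?** Fix the true cumulative incidence of response at 36.8% by week 48 (eight scans). Assume a progression or death probability q per 6-week interval (not given in the documents; 10% to 30% used), and censor at the progression scan. With response probability r_k at scan k among those at risk, 1 − KM = 1 − Π(1 − r_k), while cumulative incidence = Σ S_(k−1) r_k with S_k = S_(k−1)(1 − r_k − q) and S_0 = 1.

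- Early responses (response hazard in ratio 1 : 0.5 : 0.25 over the first three scans, then none). At q = 10%, 1 − (1 − 0.254)(1 − 0.127)(1 − 0.064) = 39.0%. At q = 30%, 1 − (1 − 0.292)(1 − 0.146)(1 − 0.073) = 43.9% before rounding the hazards. No median is reached.
- Constant response hazard. At q = 10%, r = 0.084 and 1 − (1 − r)^8 = 50.6% before rounding r, with a median at week 48. At q = 30%, r = 0.176 and the result is 78.8%, with a median at week 24.

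With progression and death as competing events, all these settings return 36.8% and no median.

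**3. Date of response.** SAP 5.5.3.1 requires the two determinations to be more than 4 weeks apart. If the TtR sentence meant the confirming scan, each responder's time would be more than 28 days longer and would end after DoR had begun. If it means the first scan of a response that is later confirmed, it agrees with SAP 5.5 and with DoR.

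**4. Eligibility date.** SAP 3.2 places eligibility within screening ("all eligibility criteria are met as confirmed by approver during screening assessments"), and Protocol 4.1.4.1 ends screening before day 1 ("Patients will be screened within a period of not more than 21 days"). The date therefore falls up to 21 days before time zero. SAP Tables 5 and 6 censor patients without a complete baseline assessment on the first day of treatment. A related case is a living patient with a baseline scan only. SAP 3.4 can admit such a patient after one 3-week cycle, while the first scan is due at week 6. If the last assessment means the last tumor assessment, this patient is also censored before day 1.

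**The case against.** The strongest reply is that the plan nowhere says progression is censored at the progression scan. The latest of the listed dates applies. Clinically stable patients are rescanned 4 to 8 weeks after progression (Protocol 8.1.2), and a patient who dies is censored at death. Progressed patients may therefore stay in the risk set long enough for the excess to shrink or vanish. This stands, and it is why the size is a range starting at zero. It does not rescue the method: the excess is zero only if every such patient remains at risk until the last response. The rule also makes the risk set depend on survival, because a progressed patient who later dies stays until death while one still alive leaves at the last assessment. And because RECIST 1.1 response is not derived after the first iUPD, the last assessment could also be read as the progression scan.

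It is also fair to say that TtR is descriptive and secondary, that ORR has its own estimate with a Clopper-Pearson interval, and that nothing presents the TtR curve as a response rate. A reader might infer that the curve must contradict the ORR; the documents support only that it can.

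Three further inferences go too far:

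- That the response-date sentence breaks the SAP's own rule. It can be read consistently with SAP 5.5 and with the definition in its own section, so it is an ambiguity.
- That any patient without a baseline scan gets a negative time. The latest-date rule means this also needs no later assessment and no death. Measurable disease at entry makes it rare, and moving the date to day 1 leaves the curve unchanged.
- That every iUPD ends the chance of an iRECIST response. Protocol 10.2.6 lets iUPD resolve to iSD, iPR or iCR, so this does not hold for iTtR.

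**Conclusion.** The concern holds for the estimator. In an all-patient TtR curve, death is explicitly censored and progression is censored by implication, although neither kind of patient can later contribute a RECIST 1.1 response. One minus Kaplan-Meier can then overstate the response proportion, by 0 to 11 points in the 52-patient example. A false median is possible if responses continue to accrue over time and progressed patients leave the risk set at the progression scan. It did not appear in the example or in the early-response settings. These sizes rest on assumed response and progression patterns and are not predictions for this trial.

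The primary ORR, the sample size and the futility rule do not use TtR and are unaffected. The response-date wording and the eligibility-date clause are clarifications only.

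**What to change.** In SAP 5.5.3.6, with matching text in Protocol 9.3.3.1:

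- Summarise TtR among confirmed responders: number, median and range. This describes timing only; the ORR already describes frequency.
- If an all-patient curve is wanted, replace Kaplan-Meier by cumulative incidence, with progression and death as competing events. For iTtR, the competing events should be death and progression that counts under the iTtP rule in SAP 5.5.3.7, not every iUPD.
- State that TtR is dated at the first scan of a response that is later confirmed, as in SAP 5.5 and for DoR.
- If an all-patient analysis is kept, replace the eligibility date by the first day of study treatment for patients with no baseline or no post-baseline scan, in line with Tables 5 and 6.

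The cost is a few sentences, an entry in SAP section 6 if the protocol is not amended, and minor programming. No additional data are needed.
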